10.1 Handling of the BLQ and the No Reportable Concentration Values	20

10.2	Handling of the Difference Between the Scheduled and the Actual Sampling Times	20
10.3	Efficacy/Pharmacodynamic Parameters	20
10.4	Statistical Analyses	21
10.4.1	Similarity Acceptance	22
10.4.2	RIG vs. SYN023 Comparison by Timepoint	22
11.	Immunogenicity: Anti-SYN023 Antibodies Analyses	23
11.1	Immunogenicity Parameters	23
11.2	Statistical Analyses	23
12.	Pharmacokinetic Analyses	23
12.1	Handling of the BLQ and the No Reportable Concentration Values	23
12.2	Handling of the Difference Between the Scheduled and the Actual Sampling Times	23
12.3	Pharmacokinetic Parameters	24
12.4	Statistical Analyses	25
13.	Data Handling	25
14.	Handling of Missing Data	25
15.	Software to be Used	25
16.	Reference List	26

LIST OF ABBREVIATIONS

Abbreviation	Term
AE	Adverse event
ALT	Alanine aminotransferase
ALP	Alkaline phosphatase
ANOVA	Analysis of variance
AST	Aspartate aminotransferase
AUC_{0-t}	Area under the concentration- time curve from time 0 to the last measurable concentration (equivalent to AUC _{0-last})
AUC_{0-inf}	Area under the concentration-time curve from time 0 to infinity
AUEC_{0-t}	Area under the effect-time curve above the minimum rabies virus neutralizing activity threshold (0.5 IU/mL) from time 0 to the last measurable concentration
AUEC_{14-t}	Area under the effect-time curve above the minimum rabies virus neutralizing activity threshold (0.5 IU/mL) from time 14 days to the last measurable concentration
BLQ	Below the lower limit of quantitation
BMI	Body Mass Index
CI	Confidence Interval
C_{max}	Maximum observed concentration
Clp	Plasma clearance
Clp/kg	Plasma clearance normalized for the subject body weight in kg
CRF	Case report form
CPK	Creatinine phosphokinase
CSR	Clinical Study Report
CV	Coefficient of variation
ECG	Electrocardiogram
E_{max}	Maximum observed effect
GLM	Generalized Linear Model
HR	Heart Rate
IG	Immune Globulin
IU	International units
K_{el}	Terminal elimination rate constant (equivalent to λ_z)
K_{el Lower}	The actual sampling time where K _{el} calculation begins
K_{el Upper}	The actual sampling time of the last measurable concentration used to estimate the K _{el}
kg	Kilogram
Max	Maximum

MedDRA	Medical dictionary for regulatory activities
Min	Minimum
mL	Milliliter
PD	Pharmacodynamic
PK	Pharmacokinetic
PP	Per Protocol
% \geq 0.5 IU/mL	Percentage of subjects with RVNA values \geq 0.5 IU/mL
PT(INR)	Prothrombin time (international normalized ratio)
PTT	Partial thromboplastin time
QI	Qualified Investigator
RVNA	Rabies virus neutralizing activity
RIG	Rabies immune globulin
RVa	RabAvert®
RVi	Imovax®
SAE	Serious adverse event
SAP	Statistical analysis plan
SAS	Statistical Analysis System
SD	Standard Deviation
SOC	System organ class
SOP	Standard operating procedure
T_{max}	Time of maximal observed plasma concentration
T_{max,E}	Time of maximum observed effect
T_{1/2 el}	Terminal elimination half-life
VR	Ventricular Rate
WHO DDE	World Health Organization Drug Dictionary Enhanced

1. Introduction

This statistical analysis plan (SAP) is intended to give a detailed description of the summaries and the analyses that will be generated for the present study by inVentiv. Analyses specified in this plan are based on Synermore Biologics Co., Ltd study protocol No. SYN023-002, dated June 21, 2016 (inVentiv Project No. 162009). Safety, tolerability, pharmacokinetic (PK) and Pharmacodynamic (PD) analyses will all be described.

The plan may change due to unforeseen circumstances and any changes made after the plan has been finalized will be documented. If additional analyses are required to supplement the planned analyses described in the SAP, the changes and justification for the changes will be outlined in the clinical study report (CSR). No change will be made without prior approval of the study sponsor. No revision to the SAP is required for changes that do not affect the statistical analysis methods, definitions, or rules defined in this document.

When applicable, all methodology and related processes will be conducted according to inVentiv's Standard Operating Procedures (SOPs). Protocol deviations occurring during the study will be listed.

2. Study Objectives

2.1 Primary Objective

- Compare the rabies virus neutralizing activity induced by licensed rabies vaccines Imovax[®] (RVi) and Rabavert[®] (RVa) co-administered with human rabies immune globulin (RIG) or 0.3 mg/kg of SYN023.

2.2 Secondary Objectives

- Compare the safety RVi and RVa administered with RIG or SYN023.
- Determine the pharmacokinetics of SYN023.
- Determine the immunogenicity of SYN023.

3. Study Design

3.1 General Design

This is a Phase 2 single site, randomized, blinded comparison of the immunogenicity of RVi and RVa when administered with RIG or SYN023. Up to 160 subjects are planned to be included in this study. Subjects will be randomized into one of four treatments with a ratio of 1:1:1:1 (40 subjects per treatment). All injections will be given intramuscularly.

3.2 Study Procedures

The overall schedule of procedures and assessments is provided in the protocol.

3.3 Treatment Description

Subjects will received one of the following treatments:

Treatment RVi + RIG (A):

At Day 0, subjects will receive Imovax[®] 1 mL dose co-administered with HyperRab ST[®] 0.133 mL/kg dose. A total of five doses of the vaccine (Imovax[®] 1 mL dose) should be administered on Days 0, 3, 7, 14, and 28.

Treatment RVa + RIG (B):

At Day 0, subjects will receive RabAvert[®] 1 mL dose co-administered with HyperRab ST[®] 0.133 mL/kg dose. A total of five doses of the vaccine (RabAvert[®] 1 mL dose) should be administered on Days 0, 3, 7, 14, and 28.

Treatment RVi + SYN023 (C):

At Day 0, subjects will receive Imovax[®] 1 mL dose co-administered with SYN023 0.3 mg/kg dose. A total of five doses of the vaccine (Imovax[®] 1 mL dose) should be administered on Days 0, 3, 7, 14, and 28.

Treatment RVa + SYN023 (D):

At Day 0, subjects will receive RabAvert[®] 1 mL dose co-administered with SYN023 0.3 mg/kg dose. A total of five doses of the vaccine (RabAvert[®] 1 mL dose) should be administered on Days 0, 3, 7, 14, and 28.

3.4 Subject Withdrawal and Replacement

Subjects were advised that they were free to withdraw from the study at any time. Over the course of the study, the Sponsor and Investigator or a delegate had the right to withdraw any subject from the study for one of the reasons described below; subject withdrawal will be done in accordance with inVentiv's SOP:

- Safety reason;
- non-compliance with protocol requirements;
- significant protocol deviation;

Subjects who withdraw or are withdrawn from the study after dosing will not be systematically replaced. Subjects who fail to complete the study through Study Day 28 may be replaced at the discretion of the sponsor.

4. Changes From the Protocol

For efficacy/PD analyses, AUC_{0-last} was replaced by $AUEC_{0-t}$, $AUC_{14-last}$ was replaced by $AUEC_{14-t}$, C_{max} was replaced by E_{max} , and T_{max} was replaced by $T_{max,E}$. This is standard nomenclature for such efficacy/PD parameters.

AUC_{0-inf} was removed from Efficacy/PD analyses because elimination phase cannot be calculated for rabies virus neutralizing activity (RVNA).

5. Primary and Secondary Parameters

The primary parameters will be $AUEC_{0-t}$ calculated on RVNA measured above 0.5 IU/mL. All other PD parameters will be regarded as secondary parameters (refer to Sections 10).

The safety, immunology and PK parameters will be regarded as secondary (refer to Sections 9, 11, and 12).

6. Analysis Populations

The analysis of safety and tolerability parameters will be based on the safety population detailed in Section 6.1 below. The analysis of immunogenicity (anti-SYN023 antibodies), PK, and PD parameters will be based on the Per-Protocol population detailed in Section 6.2 below.

6.1 Safety Population

The safety population will consist of all randomized subjects who received at least one dose of a study treatment. Treatment allocation will be based on as treated principle.

6.2 Per-Protocol Population

The PP population will consist of all randomized subjects who received all scheduled doses of a study treatment and remained on study for at least 28 days without major protocol violation. Treatment allocation will be based on as treated principle.

7. Interim Analyses

A review of Rabies Virus Inhibitory Activity, anti-SYN023 antibodies, SYN023 PK information and clinical safety data will be conducted following completion of Study Day 42. This review may present individual and aggregate (mean, median or 95% CI, as appropriate) and change from pre-study drug to each post administration time point by individual or in aggregate. Study procedures and monitoring practices will not change following this preliminary review. No decision cut points or stopping rules will be stipulated. No hypothesis testing will be performed. The purpose of this review is to obtain preliminary data for use in the decision-making process regarding Study Drug dose level. Personnel at the research site and at the immunology laboratory will remain blinded to all study results and to treatment assignments until after the Study Day 112 data have been collected, reviewed and queries resolved.

8. Study Population and Exposure

Shells for all summary descriptive statistic tables and listings referred to in this section are displayed in a separate document; the shells may be revised as they are presented to illustrate the general layout of data to be included in the final report.

No inferential analyses will be done.

8.1 Subject Disposition

Subject disposition will be summarized by treatment groups (frequency and the percentage of subjects) and overall and listed by subject. The reason for discontinuation will be also listed.

8.2 Protocol Deviations

The protocol deviations will be collected in the categories as outline on the CRF; these will be listed by subject.

8.3 Demographics and Baseline Characteristics

The descriptive statistics (mean, median, standard deviation [SD], minimum [Min], maximum [Max], and sample size) will be calculated for continuous variables (age, body mass index [BMI], height, and weight). Frequency counts and percentages will be tabulated for categorical variables (age group, gender, ethnicity, and race). All summaries will be presented overall and by treatment groups. All demographic characteristics will be listed by subject.

8.4 Medical History

All conditions that existed prior to administration of the study drug (pre-existing conditions) will be recorded in the subject's medical history to establish baseline. Medical history will be listed by subject. The Medical Dictionary for Regulatory Activities (MedDRA[®]) Version 19.1 will be used to classify all medical history findings by System Organ Class (SOC) and Preferred Term (PT).

8.5 Prior and Concomitant Medications

The use of concomitant medications will be monitored throughout the study. The World Health Organization Drug Dictionary Enhanced (WHO DDE) Version Sep2016, format B will be used to classify all medication reported during the study.

Prior and concomitant medications will be listed by subject.

8.6 Study Drug Administration

The study vaccine administration details, including treatment received, location of administration, and date and time of administration, will be listed by subject.

9. Safety Analyses

Safety and tolerability to SYN023 will be evaluated through the assessment of adverse events (AEs), clinical laboratory parameters, ECGs and vital signs measurements, clinical signs and symptoms from physical examination. AEs, clinical laboratory parameters, ECGs and vital signs measurements will be summarized by treatment groups and timepoint of collection.

Shells for all summary descriptive statistic tables and listings referred to in this section are displayed in a separate document; the shells may be revised as they are presented to illustrate the general layout of data to be included in the final report.

Safety data will be summarized but will not be subjected to inferential analysis.

9.1 Physical Examination Findings

A physical examination will be performed at screening. A focused physical examination will be performed on Day 0 till Day 112. New or worsened abnormalities will be recorded as AEs, if judged appropriate by the QI or Medical Sub-Investigator.

Any abnormal findings judged to be clinically significant will be documented as medical history or as an AE, depending upon time of observation, as appropriate. Any physical examination findings documented as AEs will be included in the AE analyses.

9.2 Solicited Adverse Events and Injection Site Reactions and Unsolicited Adverse Events

An AE is defined as any unfavorable or unintended sign, symptom, disease, syndrome, abnormal laboratory finding, or concurrent illness that emerges or worsens after receipt of study drug relative to the subject's pre-treatment baseline, whether or not it is considered to be related to the medicinal product.

The MedDRA[®] dictionary Version 19.1 will be used to classify all AEs reported during the study by SOC and PT.

9.2.1 Solicited Adverse Events and Injection Site Reactions

Solicited AEs will be events the subject is specifically asked about. These AEs are commonly observed soon after injection of study antibody. The solicited AE reporting period begins with the day of vaccination (Day 0) through Day 28 inclusively. Solicited local AEs to be collected include the following: injection site (s) pain, tenderness, redness swelling, warmth, skin disruption and regional lymphadenopathy. Non-local solicited AEs include headache, arthralgia, myalgia, rash, pruritus, urticaria, dyspnea, chest pain, cough, fever and chills. Solicited AEs of local injection site reactions (i.e., pain at injection site, redness at injection site, or swelling at injection site) will be considered causally related to study vaccine (adverse reaction).

Summary of descriptive statistics for solicited AEs (incidence of subjects with percentages and incidence of solicited AEs) will be presented by treatment and overall, SOC, PT, by investigator-assessed relationship (Not Related, Unlikely Related, Possible, Probable, and Definite) and

severity (Mild, Moderate, and Severe). For incidence of subject calculations, each subject may only contribute once to each of the incidence rates, for a solicited AE following a given treatment, regardless of the number of occurrences; the highest severity or highest relationship will be presented, as appropriate.

In each table, SOC will be presented in descending order of overall incidence rate in terms of frequency of subjects and then in frequency of events (alphabetical order will be used in case of equal rates). For each SOC, PT will be presented the same way.

All solicited AEs will be listed.

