### **3.5 Medicinal Product and Study Drug Administration**

There are four substances administered as part of this study. There are two study drugs SYN023 and rabies immune globulin (RIG): HyperRab ST® Grifols. SYN023 is investigational agent that has been administered previously to human subjects in a Phase 1 trial. RIG is licensed and

commercially available. SYN023 was tolerated acceptably in the initial human study thus enrollment of this study may be parallel between the different study groups. Vaccination will occur within 75 minutes after Study Drug administration. RVi, RVa, SYN023 and RIG will be administered by intramuscular injection. Generally antibodies should be administered on the right side of the body and vaccinations on the left side of the body to avoid administration in the same site.

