### **3.5.1 SYN023 (Study Drug)**

One or more IM injections of the calculated dose of SYN023 should be administered in any of the acceptable injection sites on the RIGHT side of the body on Study Day 0. If for some reason left sided administrations sites must be used a record must be kept of the site and care taken to not administer SYN023 at a rabies vaccination site. SYN023 is supplied at a concentration of 10 mg/mL. For example a dose calculation for a 70 kg person receiving SYN023 at the dose of 0.3 mg/kg would require a dose of 21mg resulting in a dose volume of 2.1 mL. This would need to be administration into injection sites as described below. A needle no smaller than 21-gauge and 1.0 to 3.0 inches in length depending on subject size should be used to draw up the dose of SYN023. Aspiration of SYN023 from the vial should be done gently to avoid foaming.

SYN023 is to be administered as one or more IM injections in one of three possible injection site: the gluteus medius (ventrogluteal injection site/hip), the vastus lateralis (thigh), rectus femoris (thigh) and the deltoid muscle. Doses of up to 5 mL may be given as a single injection into the hip and thigh muscles. Doses up to 3 mL may be given if required in the deltoid muscle. No more than one injection may be administered into each muscle. Only a single deltoid administration is permitted in any subject. Injections into the gluteus maximus (buttocks) will not be performed.

When selecting the site of injection, known paths of nerves, arteries and veins are to be avoided. If available ultrasound assessment of thickness of fat pad and survey of nerve and blood vessel paths may be employed. The needle should be inserted into the skin at a 90° angle. Before SYN023 is administered, aspirate gently by pulling back on the plunger. If blood is drawn into the syringe, the needle is in a blood vessel and must be moved. Remove the needle from the muscle, re-insert it in a new location in the same muscle, and repeat the aspiration step before administering SYN023. If a dose of SYN023 is drawn up and cannot be administered immediately, the syringe may be stored at 2° to 8° C and used within 3 hours.

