### **3.5.3 Rabies Vaccine RVa (Chicken Fibroblast Rabies Vaccine RabAvert®)**

The 1 mL dose of the chicken fibroblast rabies vaccine should be administered on the LEFT side of the body in Left deltoid muscle or in the Left vastus lateralis (thigh) or rectus femoris (thigh). Five doses of the vaccine should be administered on Study Days 0, 3, 7, 14 and 28. The vaccine should be administered as soon as possible after dose constitution. RVa should be administered within 75 minutes after Study Drug.

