## **5.7 Solicited Adverse Events and Injection Site Reactions**

Solicited adverse events are events the subject is specifically asked about. These adverse events are commonly observed soon after receipt of study antibody. For this study, solicited adverse events to be collected include: to be collected include the following: injection site (s) pain, tenderness, redness swelling, warmth, skin disruption and regional lymphadenopathy. Non-local solicited symptoms include headache, arthralgia, myalgia, rash, pruritus, urticaria, dyspnea, chest pain, cough, fever and chills. Solicited adverse events of local injection site reactions (i.e., pain at injection site, redness at injection site, or swelling at injection site will be considered causally related to study drug (adverse reaction).

**The reporting period during which *solicited* adverse events will be evaluated is specified in Table 3.1-1.** The solicited adverse event reporting period begins with the day of vaccination. Adverse events and solicited adverse events including assessment of local injection site reactions will be assessed by the investigator for severity, causal relationship to the study drug, possible etiologies, and whether the event meets criteria as a serious adverse event (and therefore requires immediate notification to the medical monitor).

Presence of ulceration and/or scarring at the site of injection and axillary lymphadenopathy of the injection arm(s) in adults or localized lymphadenopathy (e.g., groin) of the thigh injections are considered to be adverse events that are causally related to the study drug and are of special interest. Site of injection ulceration (including presence of drainage) and axillary lymphadenopathy will be actively evaluated during each clinic visit through study day 28. These events will be recorded on the Adverse Event CRF.

In the event that the clinical presentation meets the definition of a serious adverse event, an SAER form must be completed and the event reported per protocol instructions.

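### Protocol and SAP name different products as the automatic cause of injection-site pain, redness and swelling, and no described table separates antibody-site from vaccine-site reactions

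*SAP*

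**What the plan says.** Protocol 5.7 lists the solicited local events and then fixes causality for three of them: pain, redness or "swelling at injection site will be considered causally related to study drug (adverse reaction"). Protocol 3.5 says what study drug means: "There are two study drugs SYN023 and rabies immune globulin (RIG"). The two rabies vaccines are separate products.

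SAP 9.2.1 carries the same sentence and the same three reactions, but they "will be considered causally related to study vaccine (adverse reaction"). The SAP does not define study vaccine. SAP section 4 (Changes From the Protocol) covers only the pharmacodynamic parameters.

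Both documents also rely on assessed causality. Protocol 5.7 has the investigator judge the causal relationship of local reactions to study drug, and SAP 9.2.1 tabulates investigator-assessed relationship in five grades.

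The injections are laid out so that the products can be told apart. Protocol 3.5: "Generally antibodies should be administered on the right side of the body and vaccinations on the left side of the body". If the antibody has to go on the left, Protocol 3.5.1 says "If for some reason left sided administrations sites must be used a record must be kept of the site", and Protocol 3.5.2 says the same for RIG. For the vaccine, Protocol 3.5.3 says "Five doses of the vaccine should be administered on Study Days 0, 3, 7, 14 and 28", and Protocol 3.5.4 gives the same schedule.

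SAP 9.2.1 summarises solicited events by treatment, overall, system organ class, preferred term, relationship and severity. Side, site and product are not among the strata. SAP 8.6 says that the "location of administration, and date and time of administration, will be listed by subject", but it links this to no adverse event table.

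**The concern.** There are two linked problems.

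The first is attribution. A swelling at the left-arm vaccine site is a study-drug reaction under the protocol sentence. A swelling at the right-side SYN023 site is a vaccine reaction under the SAP sentence, if study vaccine means what it says. A reader of the relationship tables would not know which rule produced them, or whether the investigator's own grade was overridden.

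The second is pooling. Comparing safety with RIG or SYN023 is a secondary objective in both documents, and SYN023 is the investigational product. All four arms receive five vaccine injections inside the solicited window. A table that counts a subject once for injection-site pain, wherever and whenever it occurred, mixes the product of interest with a background common to all arms. A difference at the antibody site is plausible, because the injected volumes differ several-fold (see the working).

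**Working it through.** The documents give no figure to reproduce here. The check compares the texts, counts injections, and adds one illustration under stated assumptions.

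**1. The two rules side by side**

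| | Protocol 5.7 | SAP 9.2.1 |
|---|---|---|
| Reactions covered | pain, redness, swelling | pain, redness, swelling |
| Automatic cause | study drug (SYN023 or RIG) | study vaccine (undefined) |
| Investigator causality | also required | also tabulated |
| Mislabelled if read literally | vaccine-site reactions | antibody-site reactions |

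Protocol 5.5 treats possible, probable and definite as related. Neither rule says which of these grades an automatically related reaction receives, so its row in the five-grade table is undetermined.

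**2. Volumes and injection counts**

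Inputs: SYN023 0.3 mg/kg at 10 mg/mL (Protocol 3.5.1); RIG 0.133 mL/kg (Protocol 3.5.2); at most 5 mL per hip or thigh injection and 3 mL in the deltoid (both sections); weight limit 90 kg (Protocol 3.2.4).

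- SYN023, 70 kg: 70 × 0.3 / 10 = 2.1 mL, as the protocol states. At 90 kg: 2.7 mL. One injection can suffice.
- RIG, 70 kg: 70 × 0.133 = 9.31 mL, as the protocol states, so at least 2 injections. At 90 kg: 11.97 mL, so at least 3.
- Volume ratio at 70 kg: 9.31 / 2.1 = 4.4.
- Vaccine share of injections: 5/6 = 83% for a single-injection SYN023 subject, and at most 5/7 = 71% for a 70 kg RIG subject.
- Over both SYN023 arms (80 subjects): 80 × 5 = 400 vaccine injections against as few as 80 of SYN023.

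All five vaccine days fall within the Day 0 to 28 solicited period. SAP 9.2.1 lets a subject contribute once to each incidence rate regardless of the number of occurrences. It also gives event counts, but not by site.

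**3. Size of the dilution (assumed risks, not from the documents)**

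Let *a* be the antibody-site risk of a given reaction and *v* the risk of the same reaction at any vaccine site, with the sites independent and *v* equal in the two antibody groups. The pooled risk is 1 − (1 − a)(1 − v), so

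pooled difference = (1 − v) × antibody-site difference.

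Take a = 10% for SYN023 and 30% for RIG, a 20-point difference:

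| v | SYN023 pooled | RIG pooled | Difference |
|---|---|---|---|
| 0% | 10% | 30% | 20 points |
| 30% | 37% | 51% | 14 points |
| 50% | 55% | 65% | 10 points |
| 70% | 73% | 79% | 6 points |
| 90% | 91% | 93% | 2 points |

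The pooled figures also hide the absolute SYN023-site rate: at v = 50%, a 55% rate is reported where 10% of subjects reacted at the SYN023 site. SAP section 9 plans no inference on safety, so the loss is descriptive and no power figure applies.

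**4. Other routes to a by-site summary**

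Protocol 7.6.1 allows further summaries by reporting period after each vaccination, but these are optional and split by time, not site. SAP 9.2.1 lists all solicited events and SAP 8.6 lists administration location. The text does not say that the event record carries a site.

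**The case against.** The best case on the other side is that this is loose terminology with little effect.

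- **Study vaccine may simply mean study treatment.** SAP 8.6, headed Study Drug Administration, speaks of study vaccine details. SAP 9.2 defines adverse events from receipt of study drug, and SAP 9.2.2 from receipt of study vaccine. Protocol 3.4 and 3.4.1 slip in the same way. This may well be the explanation, but it does not settle the rule: the term is undefined, and either reading puts both kinds of site under one automatic label.
- **The planned tables answer the stated objective.** Each vaccine is randomised with RIG or SYN023, so by-treatment totals compare regimens without bias, and attribution changes only the relationship rows. This stands. A reader might infer that local tolerability of SYN023 cannot be read at all; the documents do not support that.
- **The rule is narrow.** It names three reactions. Tenderness, warmth and skin disruption are outside it, although Protocol 5.7 separately attributes ulceration, scarring and local lymphadenopathy to study drug. So it is wrong to say that every local reaction is affected, or that the study-drug-related share is 100% under one document and 0% under the other. The 0% also needs study vaccine to exclude study drug, which the SAP does not say.
- **Pausing is not governed by the SAP.** This is correct. Protocol 6.1 uses relatedness to study drug as judged during the trial, and the SAP sentence cannot change that. What remains lies within the protocol: read literally, 5.7 makes a Grade 3 pain, redness or swelling at a vaccine site study-drug related, and 6.1 takes relatedness as an input.
- **Separation may already be possible.** The table shells are a separate document and the form is not available, so a site field or by-site output may exist. This is why the point is limited to what the text describes.

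**Conclusion.** The point holds in a limited form. The two attribution sentences conflict as written, the change is not declared, and neither is reconciled with investigator-assessed causality. Taken literally, either rule mislabels pain, redness and swelling at the other product's site in the relationship tables.

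The SYN023 versus RIG comparison of total local reactions remains unbiased within each vaccine. Under the independence assumption it is diluted by the factor (1 − v), where v is the unknown vaccine-site risk. No described table shows the SYN023-site rate. The documents give no reaction rates by site, so the size of the dilution in this trial is unknown and the range above is only illustrative. The five-of-six vaccine share applies to single-injection SYN023 subjects and should not be quoted for all arms.

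This is worth correcting because it bears on a secondary objective and costs little. It does not touch the primary analysis.

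**What to change.** 1. Reconcile Protocol 5.7 and SAP 9.2.1 into one rule that attributes each solicited local reaction to the product given at the recorded site. Use the recorded site rather than the side alone, because left-sided antibody injections are allowed. Define study vaccine or drop the term, and list any remaining departure in SAP section 4.
2. State how the rule relates to investigator-assessed causality: whether it overrides, supplements or is shown beside the assessed grade, and which grade an automatically related reaction takes.
3. Link each solicited local reaction to its injection site or side, adding the field if the form lacks it.
4. Add a descriptive table of local reactions by arm, with antibody-site and vaccine-site reactions shown separately. Keep the planned totals.
5. Check the reconciled wording for consistency with Protocol 6.1, which uses relatedness to study drug. No pausing rule is proposed here.

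The cost is wording in two documents, possibly one form field, and one extra table. If the field is missing and subjects have already been followed, the split would depend on what source records and listings hold, and the report should say how many reactions could not be assigned to a site.
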